8.3. Inclusion Criteria

Subjects must meet all of the following Imaging (determined by the core lab) and Clinical inclusion criteria:

PR-NV16099

Imaging Criteria (Core Lab Assessed)

- 1. Subject has a target intracranial aneurysm located in the internal carotid artery (up to the terminus).
- 2. Subject has a target intracranial aneurysm with an aneurysm neck ≥4mm or a dome-to-neck ratio of < 2.
- 3. Subject has a target intracranial aneurysm that has a parent vessel with diameter 1.5–5.0 mm distal/proximal to the target intracranial aneurysm.

Clinical Criteria

- 4. Subject (or subject's legally authorized representative) has provided written informed consent using the IRB/REB and Medtronic approved Informed Consent Form and agrees to comply with protocol requirements. HIPAA/data protection authorization has been provided and signed by the subject (or subject's legally authorized representative).
- 5. Age 22-80 years at the time of consent.
- 6. Life expectancy \geq 3 years
- 7. Subject has a mRS ≤ 2 at baseline to be determined by a certified independent assessor at the site
- 8. Subject has already been selected for endovascular treatment of the target aneurysm.
- 9. Subject's last recorded P2Y₁₂ reaction units (PRU) value is between ≥60 and ≤200 prior to study procedure. For OUS sites, a TEG test may be carried out instead of the PRU test (depending on PRU test availability). In cases where TEG test is carried out, the subject should have a pre-procedure therapeutic ADP% between >30% to <90%.

- 10. Subject has multiple increased risk factors for intracranial aneurysm rupture, including but not limited to, aneurysm morphology, smoking, hypertension, diabetes, age, prior and/or family history of rupture, and/or history of subarachnoid hemorrhage that may result in a benefit risk profile of endovascular treatment to outweigh the risks of intracranial aneurysm rupture during the subject's expected lifetime if left untreated.

PR-NV16099

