9.9. Follow-up Evaluations

Subjects that consented/enrolled and underwent a successful Pipeline[™] Vantage Device implant will undergo in-clinic follow-up at 30 days, 180 days, 1 year, 2 years, and 3 years. Subjects that had a Pipeline[™] Vantage device attempt but were not successfully implanted with the Pipeline[™] Vantage device at the index procedure or subsequent attempts, will undergo in-clinic follow-up at 1 year.

9.9.1. 30-Day

At day 30 post-procedure (±7 days), the following study assessments shall be performed and recorded in the eCRFs:

- Record protocol specified medications
- Record concomitant medications
- mRS assessment to be carried out by a certified independent assessor at site
- Full Neurological Exam and assessment of aneurysm symptoms (new, improved, worsened, stable)
- Assessment of Adverse events of interest

9.9.2. 180-Day

At day 180 post-procedure (± 30 days), the following study assessments shall be performed and recorded in the eCRFs:

- Record protocol specified medications
- Record concomitant medications
- DSA imaging, if done per standard of care; if DSA not performed per standard of care, subject must undergo CTA imaging.
- mRS assessment to be carried out by a certified independent assessor at site
- Full neurological exam and assessment of aneurysm symptoms (new, worsened, improved, stable)
- Assessment of Adverse events of interest

PR-NV16099

Version C

9.9.3. 1-Year

At 1-year post-procedure (±56 days), the following study assessments shall be performed and recorded in the eCRFs:

- Pregnancy test (Pregnancy test (serum or urine) only required for females of childbearing potential. Females who are surgically sterile or post-menopausal are not required to take a pregnancy test)
- Record protocol specified medications
- Record concomitant medications
- DSA imaging
- mRS assessment to be carried out by a certified independent assessor at site
- Full neurological exam and assessment of aneurysm symptoms (new, worsened, improved, stable)
- NIHSS
- Assessment of Adverse events of interest

9.9.4. 2-Year

At 2-year post-procedure (±56 days), the following study assessments shall be performed and recorded in the eCRFs:

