12.2.4. Parent Artery Stenosis

Post-procedure angiograms will be reviewed to assess stenosis in the parent artery across the entire Pipeline[™] Vantage Device implant. Vessel stenosis will be measured and judged according to the scale in **Table 12-1** in cases, where paired imaging is available for DSA. If DSA is unavailable, flow limiting stenosis (> 50%) vs. non-flow limiting stenosis (≤ 50%) will be assessed by CTA images.

Category	Degree of Stenosis
0	1–25%
1	>25 –≤50%
2	>50 – ≤75%
3	>75–100%

Table 12-1	. Stenosis Grading Scale
------------	--------------------------

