13.1. General Principles

A detailed statistical analysis plan (SAP) will be finalized prior to performing any analyses to expand upon the statistical methods presented below. Summary tables will summarize data for all subjects combined. All recorded data will be presented in the individual data listings sorted by site patient, and date of observation.

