13.4. Eligibility of Subjects, Exclusions, and Missing Data

The number and proportion of subjects eligible for and compliant with each follow-up examination will be presented. Subjects who withdraw from the study will be tabulated with reasons for withdrawal.

Missing data, which in this instance is defined as data that was not entered into the EDC system for analysis, may have an impact upon the interpretation of the trial data.

The primary presentation of the results for the ITT population will be based on the observed data with multiple imputation for missing endpoint data using SAS PROC MI. This procedure uses an iterative modeling approach to generate estimates for patients who withdraw prematurely, incorporating multivariate imputation by fully conditional specification (FCS) methods. The discriminant function method will be used for classification variables. With the function method of classification, the missing values will be imputed sequentially in the following order: age, gender, aneurysm diameter and location (ICA: yes or no). Additional sensitivity analyses will also be conducted using the last observation and the post-procedure observation carried forward. A tipping point analysis will also be conducted.

Rules for imputing a full date for interventions with incomplete or missing start-dates will be addressed in detail in the Statistical Analysis Plan.

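### The primary multiple imputation names only baseline variables and leaves out the required 180-day core-lab occlusion result

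*Combined protocol and SAP*

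**What the plan says.** Section 13.4 bases the primary ITT presentation on observed data plus multiple imputation of missing endpoint data, by fully conditional specification in SAS PROC MI. It gives one list of variables: "the missing values will be imputed sequentially in the following order: age, gender, aneurysm diameter and location (ICA: yes or no". It also fixes the method: "The discriminant function method will be used for classification variables". The sensitivity analyses are a tipping-point analysis and two carried-forward analyses: "Additional sensitivity analyses will also be conducted using the last observation and the post-procedure observation carried forward".

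On 180-day imaging, section 9.9.2 says "if DSA not performed per standard of care, subject must undergo CTA imaging". This covers implanted subjects. Those with an attempted but failed implant have a shorter schedule: section 9.9 says that subjects not implanted "at the index procedure or subsequent attempts, will undergo in-clinic follow-up at 1 year". Sections 5.1.2.1 and 12.2.3 have the core lab grade occlusion on follow-up imaging.

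Inclusion criterion 1 in section 8.3 reads "Subject has a target intracranial aneurysm located in the internal carotid artery (up to the terminus", so ICA yes/no does not vary among eligible subjects. Section 13.1 leaves room for more detail: "A detailed statistical analysis plan (SAP) will be finalized prior to performing any analyses to expand upon the statistical methods presented below". That later plan is not part of these documents.

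**The concern.** Of the four variables named, only age, gender and diameter can carry information. On those, two subjects without 1-year imaging who are alike at baseline get the same imputed chance of success, even if one aneurysm was closed at 180 days and the other was still filling.

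The protocol's own background suggests that the 180-day result says much about the 1-year result: PUFS, PREMIER, SHIELD and PFLEX (sections 4.2.2, 4.2.5, 4.2.7 and 4.2.8) all report no recurrence. If subjects with one 180-day result are more likely to miss the 1-year image, the observed subjects are a skewed sample, and imputation from baseline variables reproduces the skew. The study's headline effectiveness rate then carries a bias that images already required could mostly remove.

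**Working it through.** **The plan's own figures.** With a 50% threshold, one-sided 2.5% and an exact binomial test, N = 100 needs at least 61 successes (lower bound 50.73%; 60 gives 49.72%), with actual type I error 1.76%. Power at 65% is 82.76% (stated 82.8%). N = 80 needs 50; power at 67% is 83.54% (stated 83.5%). Both reproduce.

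**Inputs from the documents**
- Missing 1-year occlusion data, m: PREMIER 3/141 = 2.1%; PFLEX 3/50 = 6.0%; SHIELD 16/204 = 7.8%, of whom up to 4 were failed implants. Section 13.2 expects at least 80 of 100 images, so up to 20%.
- Successful at 180 days, q: PUFS 78/106 = 73.6%. The upper end is PITA, 28/30 = 93.3%.

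**Assumptions not in the documents**
- Missingness is 2 or 3 times as likely in one 180-day group.
- One-year success is 95-100% if successful at 180 days and 35-50% if not. The pairs 95/50, 100/50 and 95/35 give gaps of 45, 50 and 60 points.
- The lower end for q is 60%.
- Age, gender and diameter carry no information about 180-day status. If they carry some, the bias is smaller.

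**Formula.** Let r be the missingness rate in the unsuccessful group divided by that in the successful group.
- Missingness in the successful group: m1 = m / (q + r(1 - q)).
- Share of the successful group among those observed at 1 year: q' = q(1 - m1) / (1 - m).
- Bias = (q' - q) x gap.

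**Worked case.** m = 0.0784, q = 0.7358, gap 0.60.
- r = 3: m1 = 0.0784/1.5283 = 0.0513; q' = 0.7358 x 0.9487/0.9216 = 0.7575; bias = 0.0217 x 0.60 = +1.30 points.
- r = 1/3: m1 = 0.0952; q' = 0.7225; bias = -0.80 points.

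Bias in percentage points, q = 78/106, gap 60:

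| Missing at 1 year | Ratio 3, either direction | Ratio 2, either direction |
|---|---|---|
| 2.1% | -0.21 to +0.33 | -0.15 to +0.20 |
| 6.0% | -0.60 to +0.97 | -0.43 to +0.59 |
| 7.8% | -0.80 to +1.30 | -0.57 to +0.79 |
| 20% | -2.36 to +3.82 | -1.68 to +2.31 |

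Bias is proportional to the gap. At ratio 3, each 10 points of gap adds -0.13 to +0.22 at 7.8% missing and -0.4 to +0.6 at 20%. At 7.8% and ratio 3, q = 60% gives -1.11 to +1.36 and q = 93.3% gives -0.22 to +0.56.

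A separate calculation assumed 60% occluded at 180 days, 1-year success of 92% versus 37%, and 20% missing. It gave 0 when missingness was equal in the two groups, +2.1 points for 15% versus 27.5% missing (occluded versus not), +4.1 for 10% versus 35%, and -2.1 for 25% versus 12.5%.

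**Does the remedy work?** Simulation with N = 100 including 2 failed implants:
- Imputing within the two 180-day groups left -0.18 to +0.06 points over 2.1-20% missing, when every lost subject had a 180-day image.
- If half of the lost subjects lacked that image, about half the bias stayed: -0.43 to +0.55 at 7.8%, -1.12 to +1.64 at 20%.
- At 20% missing, success 95%/35% and ratio 3, root mean square error fell from 5.6 to 4.5 points.
- Adding the yes/no result to the discriminant function, which assumes normal predictors, over-corrected: down to -0.88 at 7.8% (about -1.1 in a second simulation) and -2.53 at 20%. Logistic regression with a light prior gave -0.21 to +0.14 and -0.54 to +0.28.

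**Effect on the decision.** At predecessor composite rates of 71.67-76.71%, the chance of at least 61/100 is 99.2% to above 99.9%. With those rates lowered by 2.4 points it is 96.9-99.9%.

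**Secondary point.** Section 13.8.2.1 asks for an exact binomial bound, and no rule says how imputed data sets are combined into it. If imputed values are counted as observed, one-sided type I error at a true 50% with N = 100 rises from 2.0% (5 missing) through 2.5% (10 missing) to 3.2% (20 missing).

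**The case against.** The strongest reply is that 13.4 states an order of imputation, not a predictor set. It does not even name the endpoint, so the list may not be closed, and section 13.1 lets the SAP add to it. That is fair, and the SAP cannot be checked here. But this is the only variable list given for the primary analysis, and a predictor added after outcomes are seen would look data-driven.

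Second, the plan is not unprotected. Last observation carried forward uses the 180-day image where it is the last one, and the tipping-point analysis shows how many imputed outcomes would reverse the result. This stands as protection of the conclusion. Neither analysis corrects the primary estimate.

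Third, the decision is robust. At 7.8% missing, 92 observed subjects at 71.67-76.71% give 65.9-70.6 expected successes against a bar of 61, so at those expected counts the endpoint is met even with every missing subject scored a failure. This stands; it does not extend to 20% missing.

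Fourth, the size rests on assumptions. PUFS (73.6% at 180 days, 86.8% at 1 year, no recurrence) implies roughly (86.8 - 73.6)/(100 - 73.6) = 50% later success, hence a gap nearer 50 and -0.7 to +1.1 points at 7.8%; definitions and denominators there differ. PREMIER's 2.1% missing gives only -0.2 to +0.3. SHIELD is a loose anchor, because its visits were not mandated and 171 of 204 returned at 1 year while 188 had occlusion data. CTA at 180 days may agree imperfectly with DSA at 1 year. Raymond-Roy class is not the same split as the PUFS composite. Retreatment is known from site records without imaging. All of these affect the size, not whether the better predictor should be named.

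**Conclusion.** The concern holds. The primary imputation as written names no post-baseline variable, while a required, core-lab-graded 180-day result is available for implanted subjects. Under the stated assumptions, the bias is about one point or less in either direction at the missing rates of predecessor studies (at most -0.8 to +1.3), and -2.4 to +3.8 points at 20% missing. It is zero if missingness is unrelated to 180-day status, and its direction cannot be known in advance. At predecessor success rates it alters the reported rate and would not by itself change whether the endpoint is met. It should be changed because the better method is cheap and uses data already planned. Confidence is medium, since the missingness pattern and the 180-day to 1-year association are assumed. The combining-rule point is separate and is not needed for this conclusion.

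**What to change.** In section 13.4:
- Name 180-day core-lab occlusion (Raymond-Roy class 1 versus 2/3, to avoid sparse cells) as a predictor of the missing 1-year effectiveness endpoint.
- Impute that endpoint within the two 180-day groups or by logistic regression, in place of the discriminant function.
- If stenosis is added, use only two levels, split at 50%, because CTA gives nothing finer. Section 12.2.4 says "If DSA is unavailable, flow limiting stenosis (> 50%) vs. non-flow limiting stenosis (≤ 50%) will be assessed by CTA images".
- Let the fully conditional specification impute the 180-day result for implanted subjects lost before that visit. Do not impute one for failed implants as if they had been implanted; state separately how their endpoint is set.

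In the SAP, before outcomes are seen, state how imputed data sets are combined into the exact bound so that between-imputation variance counts. One option is an exact bound at effective sample size p(1 - p)/T, with T the total variance from Rubin's rules, capped at N. In simulation this held type I error at 1.9-2.2%.

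The cost is a few sentences and minor programming. The images and gradings are already planned. The combining rule makes the bound slightly wider when data are missing.

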13.5. Justification of Pooling

This study will be powered statistically based on the primary efficacy and safety endpoint. To assess poolability of the data across study sites and other predefined factors that may affect outcome, a threshold of 0.10 will be used. The testing strategy and exact model for analysis will be included in the Statistical Analysis Plan (SAP). In summary, a generalized linear model will be used, specifying the dependent variable as dichotomous and the distribution as binomial. The exact location of the aneurysm will be included in the class statement, provided each location has \geq 2 patients. Aneurysm size will be introduced into the model as a continuous variable. Separately, aneurysm size will be examined around prespecified thresholds to determine if location is a significant predictor of outcome. If clinical site, or any predefined factor is found to be a significant predictor of outcome (p<0.1), the factor will be retained

ADVANCE Clinical Investigation Plan			
PR-NV16099	Version C	Page 111 of 144	Mecttronic

in the model and adjusted confidence intervals will be derived as a secondary examination of the primary endpoint.

Small clinical sites (i.e., clinical sites that have less than 4 patients) will be identified and the following method will be used for combining the data. Data from all small clinical sites will be combined to form a single clinical site in the evaluation of clinical site interaction effects. Once combined, the pooled clinical site will remain as such for all analyses for which a clinical site interaction effect is determined. If the pooled smaller clinical sites represent a single clinical site that has more than twice as many patients as the largest single clinical site, however less than 3 times as many patients, the small clinical sites will be ranked by size and then by clinical site number and divided into 2 pooled assignments using an alternating treatment sequence (ABABAB). If the pooled smaller clinical site, however less than 4 times as many patients, the small clinical sites will be ranked by size and then by clinical sites will be ranked by size and divided into 3 pooled assignments using an alternating treatment sequence (ABCABCABC). This methodology will be applied, based on the initial pooling of the smaller clinical sites. If the pooling of smaller clinical sites results in a pooled clinical site that still has less than 4 patients, the smallest clinical site that was not included in the pooling procedure will be included and the procedure repeated.

13.6. Subgroup Analysis

Sub-group analysis will be performed based on aneurysm location and size. Note that the subgroup analyses listed here are not independently powered and they are for exploratory purpose only. Statistical testing analogous to the above (Section 13.5) will be performed to assess poolability of these subgroups into the overall study results. The incidence for the primary efficacy and primary safety endpoints will be derived and summarized without adjustment for other factors. A secondary examination will be performed where aneurysm location and aneurysm size will serve as covariates in an adjusted model. It is indeterminate if there will be sufficient power to discriminate across these 2 factors, given the enrollment into the study will not be controlled for either factor. A series of derived estimates will be generated for the primary efficacy and safety endpoints retaining aneurysm size and anatomical location as a secondary examination of the primary endpoint. All factors and method of analysis will be clearly defined in the SAP.

13.7. Interim Analysis

No formal interim analyses are planned for the purpose of stopping this trial early for effectiveness.

13.8. Statistical Analysis

All statistical analyses will be done using the SAS System software, version 9.4 or later (SAS Institute Inc., [name]).

PR-NV16099

Version C

13.8.1. Demographics, Clinical Baseline and Procedure Characteristics

Patient demographics, clinical history, risk factors, aneurysm characteristics, procedure characteristics, and outcome variables will be summarized using descriptive statistics for continuous variables (mean, standard deviation, number of observations, minimum and maximum) and frequency tables for discrete variables.

13.8.2. Primary Endpoint Analysis

13.8.2.1. Primary Effectiveness Endpoint

The pre-specified threshold of 50% for effectiveness endpoint is based on the effectiveness threshold of the recent PREMIER study with the Pipeline[™] Device. This threshold must be exceeded at a certain magnitude to reject the null hypothesis and merely serves a statistical boundary for analysis. If the upper bound of the 1-sided 97.5% exact binomial confidence interval is >50%, the primary effectiveness endpoint will have been met.

To ensure at least 95% power with 80 and 100 patients, the observed incidence of complete aneurysm occlusion without parent artery stenosis or retreatment would need to be a minimum of 71% and 69%, respectively. Requiring a minimum sample size of 100 patients with 95% power translates into a minimum incidence of complete aneurysm occlusion without parent artery stenosis of 69% which is relatively inline with the previous results with the results from previous Pipeline studies.

The primary effectiveness endpoint is the incidence of complete aneurysmocclusion (Raymond Roy Scale Class 1) without significant parentartery stenosis (≤50%) or retreatment of the target aneurysm at 1-year post-procedure. The incidence will be summarized using counts and percentages; the 1-sided upper bound of the 97.5% confidence limit for the incidence will be evaluated relative to the a priori threshold of 50%. The hypothesis for evaluating the primary effectiveness endpoint is stated below:

 H_o : Incidence at 1-year post-procedure of complete aneurysm occlusion without retreatment or significant parent artery stenosis is \le 50.0%

 $H_a:$ Incidence at 1-year post-procedure of complete aneurysm occlusion without retreatment or significant parent artery stenosis is >50.0%

If the upper bound of the 1-sided 97.5% exact binomial confidence interval is >50%, the primary effectiveness endpoint will have been met.

All eligible patients will undergo follow-up at 12 months.

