stenosis (≤ 50%) or retreatment of the target aneurysm at 1-year post- procedure. The incidence will be summarized using counts and percentages; the 1-sided upper bound of the 97.5% confidence limit for the incidence will be evaluated relative to the a priori threshold of 50%. The hypothesis for evaluating the primary effectiveness endpoint is stated below: H _o : Incidence at 1-year post-procedure of complete aneurysm occlusion without retreatment or significant parent artery stenosis is ≤ 50.0% H _a : Incidence at 1-year post-procedure of complete aneurysm occlusion without retreatment or significant parent artery stenosis is > 50.0% The pre-specified threshold of 50% for effectiveness endpoint is based on the effectiveness threshold of the recent PREMIER study with the Pipeline™ Device. This threshold must be exceeded at a certain magnitude to reject the null hypothesis and merely serves a statistical boundary for analysis. If the upper bound of the 1-sided 97.5% exact binomial confidence interval is >50%, the primary effectiveness endpoint will have been met.
primary effectiveness endpoint wirnave been met.
Sample Size The target sample size for this clinical investigation is 100 patients enrolled and
treated and followed for safety events with the expectation of having digital imagery at 1-year post-procedure on a minimum of 80 patients. To calculate
the sample size, simulations were prepared in SAS assuming an observed incidence in the ADVANCE IDE study of primary safety events ranging from 5.6%
to 6.9%. With 100 patients and an observed incidence of safety event from 5.6% to 6.4%, the power exceeded 80%. Between the ranges of 6.5% to 6.9%, the power ranged from 79.8% to 74.7% for the primary safety endpoint and
slightly below 80%. Although the power is less than 80 when the incidence of safety events was 6.5% or higher, the power was still considered adequate
when contrasted against the actual upper bound of the 1-sided 97.5% exact binomial confidence interval. Specifically, if 7 of the 100 patients experience a primary safety event, the upper bound of the 1-sided 97.5% exact binomial
confidence interval would be 13.89% and below the 14% threshold. For primary effectiveness endpoint, the power was estimated for an observed
rate between 65% to 80% considering sample sizes from 80 to 100 patients. With a type 1 error rate of 2.5%, 100 patients would have 82.8% power to reject

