the null hypothesis if the observed incidence of complete aneurysm occlusion without parent artery stenosis or retreatment was 65%. Under the same
scenario with 80 patients, the power would be 83.5% if the observed incidence
of complete aneurysm occlusion without parent artery stenosis was 67%. To

Medtronic Controlled Information

PR-NV16099	Version C	Page 32 of 144	Medtronic
	ensure at least 95% power with 80 complete aneurysmocclusion with a minimum of 71% and 69%, resp previous results with the results fr	hout parent artery stenosi pectively, which is relativ	is would need to be ely in-line with the
	Statistical AnalysisWith the general exception of the threshold, all statistical tests will be level. Baseline is defined as the lat procedure.The primary effectiveness endpotic occlusion (Raymond Roy Scale C stenosis (≤ 50%) or retreatment procedure; the 1-sided lower book incidence will be evaluated relat primary presentation of the result observed data with multiple import PROC MI.The primary safety endpoint is th supplied by the treated artery or m the study procedure. The incide percentages; the 1-sided upper bo incidence will be evaluated relative	be 2-sided, performed at t ast observation recorded int is the incidence of co Class 1) without signific t of the target aneurysi und of the 97.5% confic tive to the a priori thres to for the ITT population we utation for missing endpoint e incidence of major stro neurological death record nce will be summarized ound of the 97.5% confic	the 5% significance I prior to the study omplete aneurysm cant parent artery m at 1-year post- dence limit for the hold of 50%. The vill be based on the pint data using SAS oke in the territory led within 1 year of using counts and dence limit for the

PR-NV16099

Version C

4. Introduction

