Occurrence of major stroke in the territory supplied by the treated artery or neurological death at 1-year post-procedure (primary safety endpoint) occurred in 0.0% of subjects. There were no major strokes in the territory supplied by the treated artery or neurological death at 30 days post-procedure due to procedural complications. There was no delayed intracerebral hemorrhage >30 days through 1-year post-procedure (0.0%; 0/50). The overall mortality rate was 0.0% (0/50). Summary of primary endpoints of PFLEX study is presented in **Table 4-2**.

Endpoints	Rates	1-Sided
		97.5% Exact
		Binomial
		Confidence
		Interval
Primary Effectiveness Endpoint: Complete aneurysm occlusion (defined as Raymond-Roy g	ra de 1 ¹) without	significant
parent artery stenosis (≤ 50%) or retreatment of the target a neurys mat 1-year post-proced	lure	
ITT‡ population (N=50)	73.62%	59.39%*
ICA# Population (N=47)	74.23%	59.24%*

Table 4-2. Summary of Primary Endpoints of PFLEX Study

Medtronic Controlled Information

PR-1	VV16	099
------	------	-----

Version C

Page 43 of 144

Primary Safety Endpoint: Occurrence of major stroke in the te	rritory supplied by the treated artery or ne	urological death a
1-year post-procedure		
ITT‡ population (N=50)	0.0%	7.1%†
ICA# population (N=47)	0.0%	7.5%†
*Lower Bound of the Binomial Confidence Interval		
[†] Upper Bound of the Binomial Confidence Interval		
‡Intention to Treat (ITT) population included all consented subjects in w	'hom deployment of the Pipeline™ Shield device	was attempted.
#Internal Carotid Artery Population (ICA Population) is defined as a subs	set of ITT population that included only those sub	jects in whom the
Pipeline [™] Shield device was implanted in the ICA (segments C2-C7 incl	uding the terminus).	

Overall, a high rate of complete aneurysm occlusion was achieved with the use of the Pipeline[™] Shield device in the treatment of intracranial aneurysms. The incidence of major stroke, neurological death, and delayed intracerebral hemorrhage in the PFLEX study were low. Therefore, results from the PFLEX Study demonstrated that the Pipeline[™] Shield device is effective and safe for the endovascular treatment of intracranial aneurysms.

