For the primary effectiveness endpoint, the power was estimated for an observed rate between 65% to 80% considering sample sizes from 80 to 100 patients. With a type 1 error rate of 2.5%, 100 patients would have 82.8% power to reject the null hypothesis if the observed incidence of complete aneurysm occlusion without parent artery stenosis was 65%. Under the same scenario with 80 patients, the power would be 83.5% if the observed incidence of complete aneurysm occlusion without parent artery stenosis or retreatment would need to be a minimum of 71% and 69%, respectively. Requiring a minimum sample size of 100 patients with 95% power translates into a minimum incidence of complete aneurysm occlusion without parent artery stenosis or retreatment artery stenosis of 69% which is in-line with the previous results with the results from previous Pipeline studies.

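### The primary effectiveness rule tests the upper confidence bound against 50%, so read literally 40 successes in 100 pass and the type I error is about 98%

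*Combined protocol and SAP*

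**What the plan says.** Section 13.8.2.1 tests H0: incidence ≤ 50% against Ha: incidence > 50% for complete occlusion without significant parent artery stenosis or retreatment at 1 year. It states the decision rule twice in the same words: "If the upper bound of the 1-sided 97.5% exact binomial confidence interval is >50%, the primary effectiveness endpoint will have been met". It also says that "the 1-sided upper bound of the 97.5% confidence limit for the incidence will be evaluated relative to the a priori threshold of 50"%. The synopsis (Section 3, Statistics) repeats both the evaluation sentence and the success sentence next to the effectiveness hypotheses. That makes five statements that name the upper bound.

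Other places point the other way:

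- The synopsis Statistical Analysis paragraph names the lower bound for effectiveness. The extracted text is garbled there ("the 1-sided lower book incidence will be evaluated"), but the word lower is legible, as is the 50% threshold.
- Section 13.8.2.1 says of the 50% goal: "This threshold must be exceeded at a certain magnitude to reject the null hypothesis".
- Table 4-2 (Section 4.2.8) reports the same effectiveness endpoint in the PFLEX study with the footnote "Lower Bound of the Binomial Confidence Interval", and keeps the upper bound for safety.
- Section 13.2 states the design error rate: "With a type 1 error rate of 2.5%, 100 patients would have 82.8% power".

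**The concern.** To reject a null hypothesis that the rate is at most 50%, the data must rule out rates of 50% and below, so the lower confidence bound has to lie above 50%. An upper bound above 50% is a much weaker finding: it says only that the data are compatible with some rate above 50%. The upper bound is the right one for safety (Section 13.8.2.2), where the null is an incidence of 14% or more and a low rate is good. The effectiveness wording has the same form, but the hypothesis runs in the opposite direction.

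At stake is the pre-specified pass/fail criterion for one of the two primary endpoints. The study has a single arm, so no control group would expose a wrong rule. Section 13.1 says that a detailed SAP will expand on these methods, so the error could be carried forward. If the contradiction is settled only after results are known, the choice of bound will look data-driven.

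**Working it through.** **Inputs.** Threshold 50%, one-sided 97.5% exact binomial bound (Section 13.8.2.1). N = 100 treated, with 1-year imaging expected on at least 80 (Section 13.2). Stated type I error 2.5%. Stated power 82.8% for N = 100 at 65% (Section 13.2) and 83.5% for N = 80 at 67% (power in Section 13.2; the 67% is legible in the synopsis). Minimum rates for 95% power: 71% (N = 80) and 69% (N = 100).

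**Formulas.** For x successes in n, the exact (Clopper-Pearson) bounds are:

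- lower L(x) = Beta⁻¹(0.025; x, n − x + 1)
- upper U(x) = Beta⁻¹(0.975; x + 1, n − x)

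If c is the smallest passing count, P(success) = P(X ≥ c) with X ~ Binomial(n, p). The type I error is this probability at p = 0.50.

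**Step 1: reproduce the plan's power with the lower-bound rule, L(x) > 50%.**

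| N | Cut-off c | Bound at c | Bound at c − 1 | Type I error | True rate | Power | Stated |
|---|---|---|---|---|---|---|---|
| 100 | 61 | 50.73% | 49.72% | 1.76% | 65% | 82.76% | 82.8% |
| 80 | 50 | 50.96% | 49.70% | 1.65% | 67% | 83.54% | 83.5% |

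The 95%-power minimums reproduce too. N = 80 gives 96.1% at 71% but 94.1% at 70%; N = 100 gives 96.5% at 69% but 94.4% at 68%. A normal approximation does not match the stated power (86.2% and 87.5%), so the plan's figures come from the exact lower-bound test.

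**Step 2: apply the rule as written, U(x) > 50%.**

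| N | Cut-off c | Bound at c | Bound at c − 1 | Type I error | P(success) at 45% | P(success) at 40% |
|---|---|---|---|---|---|---|
| 100 | 40 | 50.28% | 49.27% | 98.24% | 86.6% | 53.8% |
| 80 | 31 (38.8%) | 50.30% | 49.04% | 98.35% | 89.2% | 63.1% |

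Under this rule the power at 65% with N = 100, and at 67% with N = 80, is 100% to the precision computed. The stated 82.8% and 83.5% cannot come from it.

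**Step 3: cross-check by symmetry.** At p = 0.50, P(X ≥ 40) = 1 − P(X ≤ 39) = 1 − P(X ≥ 61) = 1 − 0.0176 = 0.9824. The rule as written fails only when the data show significantly that the rate is below 50%, which is the mirror image of the intended test.

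**Step 4: where the two readings disagree.** With N = 100, every count from 40 to 60 passes the upper-bound rule and fails the lower-bound rule. With N = 80 the range is 31 to 49.

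**Step 5: confirm that safety is unaffected.** For 7 events in 100 the exact upper bound is 13.89%, as Section 13.2 states. The upper bound is correct there because that null is ≥ 14%.

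**The case against.** The strongest reply is that nobody intended a 98% type I error. The hypotheses, the stated 2.5% error rate, every effectiveness power figure and the synopsis analysis paragraph all fit the lower bound. The remark that the threshold must be exceeded by some margin also sits badly with passing an observed 40%. On this view the defect is a wording slip, possibly carried over from safety. The earlier Pipeline studies described in the protocol reported 76.71%, 71.67% and 73.62% on this endpoint (Sections 4.2.5, 4.2.7 and 4.2.8). Rates at that level, observed in 80 or 100 patients, would pass either rule.

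Two technical points can be added. The cut-offs assume complete data with exactly 80 or 100 patients, whereas the primary ITT analysis uses multiple imputation (Section 13.4), so results need not be whole counts. And Section 13.1 promises a detailed SAP, which may already be correct.

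The reading of intent is persuasive and stands; it is also why the remedy is simple. It does not remove the defect. Every sentence that says when effectiveness will have been met uses the upper bound, and it does so in two sections. Imputation would change the exact cut-offs and probabilities but not the direction of the error. A correct SAP would still conflict with the protocol. That a good result would pass under either reading is no defence of a rule whose purpose is to fail poor ones.

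**Conclusion.** The concern holds. The written effectiveness rule uses the wrong bound for its own hypotheses and conflicts with the synopsis analysis paragraph, the stated 2.5% type I error and the stated power. Read literally, with complete data on 100 patients, success starts at 40/100 and the type I error at a true rate of 50% is 98.2%; with 80 patients it starts at 31/80 and the error is 98.4%. The rule that the plan's own figures imply needs at least 61/100 (type I error 1.76%) or 50/80 (1.65%). These figures rest on exact binomial calculations without multiple imputation. The cause is most probably a wording error, but because it governs a primary endpoint it must be corrected before any analysis.

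**What to change.** In Section 13.8.2.1, change upper to lower in the evaluation sentence and in both statements of the success rule. Make the same two changes beside the effectiveness hypotheses in the synopsis. The rule should then say that effectiveness is met if the lower bound of the one-sided 97.5% exact binomial confidence interval exceeds 50%, in agreement with the synopsis Statistical Analysis paragraph. Leave the upper bound for safety in Section 13.8.2.2 and its synopsis counterpart. Use the corrected wording in the SAP, and correct the SAP if it has already taken over the upper-bound text.

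The cost is a wording amendment. Patients, sample size and the stated effectiveness power are unaffected, because the power was already calculated with the lower bound.
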